7.3 Liver safety monitoring

To ensure patient safety and enhance reliability in determining the hepatotoxic potential of an investigational drug, a standardized process for identification, monitoring and evaluation of liver events has to be followed.

Hepatotoxicity-related events are subject to additional safety assessments and thus are followed with a standardized questionnaire. A list of terms that are considered “hepatotoxicity-related” (e.g., cholaemia, ascites, liver disorder) will be provided to sites in a manual.

If such an event occurs that meets criteria for serious adverse event, the investigator will complete a separate questionnaire for a Hepatotoxicity and Statin-related Event form (provided by Novartis) to summarize the event, its further diagnostic tests performed, and its related information.

Liver events are divided into two categories:

- Liver events of special interest (AESI) which consist of liver function tests (LFTs) elevations
- Medically significant liver events which are considered as serious adverse events (SAEs) and which consist of marked elevations of LFTs and / or pre-specified adverse events.

Please refer to Table 19-1 in Appendix 7 for complete definitions of liver events.

Any liver event which meets the criteria for “**medically significant**” event as outlined in Table 19-1 of Appendix 7 should follow the **standard procedures for SAE reporting** as described in [Section 7.2](#).

Every liver event as defined in Table 19-1 of Appendix 7 should be followed up by the investigator or designated personal at the trial site as summarized below. Detailed information is outlined in Table 19-2 in Appendix 7.

- Repeating the LFT to confirm elevation as appropriate
- Discontinuation of the investigational drug if appropriate
- Hospitalization of the patient if appropriate
- A causality assessment of the liver event via exclusion of alternative causes (e.g., disease, co-medications)
- An investigation of the liver event which needs to be followed until resolution.

These investigations can include serology tests, imaging and pathology assessments, hepatologist’s consultancy, based on investigator’s discretion. All follow-up information, and the procedures performed should be recorded on appropriate CRF pages, including the liver event overview CRF pages.

7.4 Pregnancy reporting

In case a patient becomes pregnant, or plans to become pregnant, the study drug must be interrupted before contraception is discontinued (or, from the date the pregnancy becomes known) for the entire duration of the pregnancy and lactation period (or, for the entire duration that contraception is discontinued). To ensure patient safety, each pregnancy in a patient on study drug must be reported to Novartis within 24 hours of learning of its occurrence. The pregnancy should be followed up to determine outcome, including spontaneous or voluntary

termination, details of the birth, and the presence or absence of any birth defects, congenital abnormalities, or maternal and/or newborn complications.

Pregnancy should be recorded on a Clinical Trial Pregnancy Form and reported by the investigator to the local Novartis DS&E Department. Pregnancy follow-up should be recorded on the same form and should include an assessment of the possible relationship to the Novartis study drug of any pregnancy outcome. Any SAE experienced during pregnancy must be reported on the SAE Report Form.

7.5 Prospective suicidality assessment

Not applicable.

8 Data review and database management

8.1 Site monitoring

Before study initiation, at a site initiation visit or at an investigator's meeting, a Novartis representative will review the protocol and CRFs with the investigators and their staff. During the study, the field monitor will visit the site regularly to check the completeness of patient records, the accuracy of entries on the CRFs, the adherence to the protocol and to Good Clinical Practice, the progress of enrollment, and to ensure that study treatment is being stored, dispensed, and accounted for according to specifications. Key study personnel must be available to assist the field monitor during these visits.

The investigator must maintain source documents for each patient in the study, consisting of case and visit notes (hospital or clinic medical records) containing demographic and medical information, laboratory data, electrocardiograms, and the results of any other tests or assessments. All information on CRFs must be traceable to these source documents in the patient's file. The investigator must also keep the original informed consent form signed by the patient (a signed copy is given to the patient).

The investigator must give the monitor access to all relevant source documents to confirm their consistency with the CRF entries. Novartis monitoring standards require full verification for the presence of informed consent, adherence to the inclusion/exclusion criteria, documentation of SAEs, and of data that will be used for all primary variables. Additional checks of the consistency of the source data with the CRFs are performed according to the study-specific monitoring plan. No information in source documents about the identity of the patients will be disclosed.

8.2 Data collection

Designated investigator staff will enter the data required by the protocol into the OC/RDC system. Designated investigator site staff will not be given access to the system until they have been trained.

Automatic validation procedures within the system check for data discrepancies during and after data entry and, by generating appropriate error messages, allow the data to be confirmed or corrected online by the designated investigator site staff. The Investigator must certify that

the data entered into the electronic Case Report Forms are complete and accurate. After database lock, the investigator will receive copies of the patient data for archiving at the investigational site.

8.3 Database management and quality control

Novartis staff, or CRO staff working on behalf of Novartis, review the data entered into the eCRFs by investigational staff for completeness and accuracy and instruct the site personnel to make any required corrections or additions. Obvious errors are corrected by Novartis personnel or CRO staff working on behalf of Novartis. Queries are sent to the investigational site using an electronic data query. Designated investigator site staff is required to respond to the query and confirm or correct the data. If the electronic query system is not used, a paper Data Query Form will be faxed to the site. Site personnel will complete and sign the faxed copy and fax it back to Novartis staff who will make the correction to the database. The signed copy of the Data Query Form is kept at the investigator site.

Concomitant medications entered into the database will be coded using the WHO Drug Reference List, which employs the Anatomical Therapeutic Chemical classification system. Medical history/current medical conditions and AEs will be coded using the Medical dictionary for regulatory activities (MedDRA) terminology.

Laboratory samples will be processed centrally and the results will be sent electronically to Novartis (or a designated CRO).

Randomization codes and data about all study drug(s) dispensed to the patient and all dosage changes will be tracked using an Interactive Response Technology (IRT). The system will be supplied by a Novartis, who will also manage the database.

At the conclusion of a non-IRT study, the occurrence of any emergency code breaks will be determined after return of all code break reports and unused supplies to Novartis. The occurrence of relevant protocol deviations will be determined. After these actions have been completed and the database has been declared to be complete and accurate, it will be locked and the treatment codes will be unblinded and made available for data analysis. Any changes to the database after that time can only be made after written agreement by Trial Statistician and Statistical Reporting and the Clinical Trial Leader.

Each occurrence of a code break via IRT will be reported to the clinical team and monitor. The code break functionality will remain available until study shut down or upon request of Novartis

8.4 Data Monitoring Committee

Not required.

8.5 Adjudication Committee

Angioedema Adjudication Committee

If an angioedema or angioedema-like event occurs, the investigator will complete an Adjudication Questionnaire for an Angioedema-like Event form (provided by Novartis). Details on the process of reporting angioedema and angioedema like events are outlined in a manual provided to investigators.

Submission of an angioedema report is not a substitution for the submission of an AE or SAE report. If an angioedema-like event satisfies the definition of an AE or SAE, the investigator must submit an AE or SAE report according to the respective processes in addition to the Adjudication Questionnaire for an Angioedema-like Event.

The membership and responsibilities of the Angioedema Adjudication Committee are defined in a separate document that will be provided to the sites.

9 Data analysis

9.1 Analysis sets

The following populations will be used for the statistical analyses:

The full analysis set (FAS) will consist of all randomized patients who have received at least one dose of study drug. Following the **intent-to-treat principle**, patients will be analyzed according to the treatment to which they were assigned at randomization. Efficacy variables will be analyzed based on the FAS as the primary population.

The Safety Population (SAF) will consist of all randomized patients who received at least one dose of study drug. Patients will be analyzed according to the treatment actually received. The safety population will be used for the analyses of safety variables.

9.2 Patient demographics and other baseline characteristics

Baseline value is defined as the last non-missing assessment prior to the first dose of randomized study medication unless specified otherwise.

Summary statistics will be provided by treatment group for demographics and baseline characteristics, including age, age group (<65 years vs. ≥65 years), sex, race, weight, height, body mass index (BMI), category of prior CHF medication, prior HF hospitalization, NYHA class, and vital signs. BMI will be calculated as weight (kg) / height² (m²) from the collected height and weight at Visit 1 (Screening Visit). Continuous variables will be summarized using n, mean, standard deviation, median, minimum, and maximum. Categorical variables will be summarized using frequency and percentage.

The FAS will be the patient population for the above analyses.

9.3 Treatments (study drug, rescue medication, other concomitant therapies, compliance)

The overall duration on the double-blind study drug will be summarized by treatment group using mean, standard deviation, median, minimum, and maximum. Additionally, the number and percentage of patients will be summarized by treatment group for duration category.

Concomitant medications and significant non-drug therapies, prior to and after the randomization date respectively, will be summarized by therapeutic class, preferred term, and treatment group for the safety population.

The number and percentage of patients on different CHF background medications (aldosterone antagonists, β -blockers, ivabradine, diuretics, digoxin) will be tabulated by treatment at baseline and during the double-blind stage.

The FAS will be used for the above analyses.

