Patients should continue to take their background medications for CHF during the study, with the exception of ACEI or ARBs which are replaced by investigational treatment and must be discontinued before first application of study drug (washout period of 36 hours applies to ACEI, compare [Section 5.5.8](#)). First application of study drug is planned on the day after Visit 3; last intake of ACEI or ARB before study drug application thus will be in the evening prior to Visit 3 (randomization) (If Visit 3 is scheduled for Wednesday e.g., last ACE or ARB medication should be taken by the patient on Tuesday evening. The patient will then start to take the first dose of LCZ696 or enalapril double blind medication on Thursday morning.).

Tolerability to study treatment will be checked at every visit after randomization. Please refer to [Section 5.5.5](#) for allowed study drug adjustments during the study. Non-disease modifying medications (such as nitrates, CCBs, α -blockers, and diuretics) may be changed (dose reduced or discontinued) in response to the occurrence of adverse events, if they are believed to be the cause of the AE such as hyperkalemia, hypotension, and renal dysfunction, in an attempt to allow patients to meet the safety criteria in Table 3-2. The dose of background disease modifying drugs, such as β -blockers, ivabradine and aldosterone antagonists, may be reduced to facilitate maintenance of study drug if they are believed to be the cause of the adverse effect in question. If necessary, in doubt patients will be titrated down to the next lower dose level of study medication twice a day as described in [Section 5.5.5](#), at the investigator's discretion, based on the defined safety and tolerability criteria (Appendix 1, Appendix 2, Appendix 3, and Appendix 4). The reason for medication modification must be carefully documented in the appropriate eCRFs. Any changes in the study drug dose level, including temporary/permanent withdrawal or restart of the study drug, must be recorded on the Dosage Administration Record eCRF.

After randomization, temporary study drug discontinuation for any reason does not automatically constitute withdrawal from the study and should not lead to the patient being withdrawn from the study. Patients should be re-challenged to receive study treatment according to guidance in [Section 5.5.5](#).

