Visit 3 (Randomization)

At Visit 3 all patients who meet all entry criteria, including the required clinical laboratory values, and meet the safety criteria in Table 3-2, will be randomized to one of the two treatment arms enalapril bid or LCZ bid add on to their current heart failure therapy.

Patients should have discontinued their ACE/ARB medical therapy in the evening before Visit 3 in order to start study drug in the morning one day later. (If Visit 3 is scheduled for e.g. Wednesday, last ACE or ARB medication should be taken by the patient on Tuesday evening. The patient will then start to take the first dose of LCZ696 or enalapril double blind medication on Thursday morning.). If the patient continued to take their usual ACEI, the start of study drug has to be postponed to assure a 36 hour washout before first application of study drug.

Patients will start study treatment at dose level 2 or 2a according to their ACE/ARB-treatment prior to study (refer to [Section 5.5.4](#) for details) and must be stabilized on this dose for 2 weeks.

To ascertain patient's eligibility, study drug should not be dispensed unless laboratory assessments of potassium and eGFR are available and meet the safety criteria (see Table 3-2).

Study medication dispense can only be done with a valid ergospirometry measurement.

Visit 4 (+ 2 weeks; up-titration visit)

After 2 weeks of treatment at Visit 4, patients will be checked for tolerability and will be up-titrated to target dose level 3 (LCZ 200 mg bid; enalapril 10 mg bid). Therefore symptomatic hypotension, renal dysfunction and/or hyperkalemia are considered to be safety parameters and should be handled according to respective guidelines for management (Appendix 1, Appendix 2 Appendix 3, and Appendix 4).

Blood draw for lab assessments has to be done. In case of lab deviations an unscheduled visit may be scheduled at the discretion of the investigator to re-assess lab parameters and evaluate the efficacy of taken measures. Please refer to Appendix 1, Appendix 2, Appendix 3, and Appendix 4, respectively, for guidance on handling hyperkalemia, hypotension, and renal dysfunction.

Visit 5 (+4 weeks)

After 2 weeks of treatment on level 3 study medication, patients will be checked for tolerability at Visit 5. Every attempt should be made to keep the patients stable on level 3 throughout the whole study in accordance with all safety parameters (e.g. symptomatic hypotension, renal dysfunction and /or hyperkalemia).

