2.4.2 Prior, concomitant and post therapies

Medications will be identified using Novartis Drug and Therapy Dictionary, NovDTD which is a modified Novartis internal version of Q3 2004 WHO Drug Reference List (DRL) including Anatomical Therapeutic Chemical (ATC) code.

The concomitant medication information for the double blind phase will be summarized based on the SAF.

Concomitant medications, significant non-drug therapies and surgical and medical procedures, prior to and after the randomization date respectively, will be summarized by treatment group based on the latest version of dictionary. Medications will be presented in alphabetical order, by ATC codes and grouped by anatomical main group (the 1st level of the ATC codes). Table

will also show the overall number and percentage of subjects receiving at least one drug of particular ATC code and at least one drug in a particular anatomical main group.

As before, concomitant medication will be identified based on recorded or imputed start and end dates of medication taking. The rules for imputing incomplete (start and end) dates are described in [Section 5.1.3](#).

Concomitant heart failure and CV medications administered during double blind period will be summarized separately, in the same way. More specifically, the following classes of medication will be summarized separately.

- Aldosterone antagonists
- β - blockers
- Ivabradine
- Diuretics
- Digoxin
- Other
- Statin
- ACEI
- ARBs

Below ATCs will be used to present ATC specific table for during and/or prior to study period:

ATC codes	Sub group	Sub sub group	Period
C CARDIOVASCULAR SYSTEM			Prior, During
	C01 CARDIAC THERAPY	C01A CARDIAC GLYCOSIDES	
		C01B ANTIARRHYTHMICS, CLASS I AND III	Prior, During
		C01C CARDIAC STIMULANTS EXCL. CARDIAC GLYCOSIDES	Prior, During
		C01D VASODILATORS USED IN CARDIAC DISEASES	Prior, During
		C01E OTHER CARDIAC PREPARATIONS	Prior, During
	C02 ANTIHYPERTENSIVES	C02A ANTIADRENERGIC AGENTS, CENTRALLY ACTING	Prior, During
		C02B ANTIADRENERGIC AGENTS, GANGLION-BLOCKING	Prior, During
		C02C ANTIADRENERGIC AGENTS, PERIPHERALLY ACTING	Prior, During
		C02D ARTERIOLAR SMOOTH MUSCLE, AGENTS ACTING ON	Prior, During
		C02K OTHER ANTIHYPERTENSIVES	Prior, During
		C02L ANTIHYPERTENSIVES AND DIURETICS IN COMBINATION	Prior, During
		C02N COMBINATIONS OF ANTIHYPERTENSIVES IN ATC-GR. C02	Prior, During
	C03 DIURETICS	C03A LOW-CEILING DIURETICS, THIAZIDES	Prior, During

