5.1.3 Concomitant medication date imputation

Date imputation for concomitant medications will be imputed according to Novartis conventions described in [\[RAP Module 8\]](#).

Concomitant medication(CMD) start date imputation (#IMPUMED)

Rules for imputing the CMD start date:

This algorithm is used when *event* is the partial start date of the concomitant medication, non-drug therapy/procedure, or prior anti-neoplastic therapy.

The following table explains the notation used in the logic matrix. Please note that **missing start dates** will not be imputed.

	Day	Month	Year
Partial CM Start Date	Not used	MON	YYYY
Treatment Start Date(TRTSDT)	Not used	TRTM	TRTY

The following matrix explains the logic behind the imputation.

	MON MISSING	MON<TRTM	MON=TRTM	MON>TRTM
YYYY MISSING	(C2) Uncertain	(C1) Uncertain	(C1) Uncertain	(C1) Uncertain

YYYY<TRTY	(D) Before Treatment Start	(A) Before Treatment Start	(A) Before Treatment Start	(A) Before Treatment Start
YYYY=TRTY	(C2) Uncertain	(A) Before Treatment Start	(C1) Uncertain	(B) After Treatment Start
YYYY>TRTY	(E) After Treatment Start	(B) After Treatment Start	(B) After Treatment Start	(B) After Treatment Start

The following table is the legend to the logic matrix.

Relationship	
Before Treatment Start	Partial date indicates CMD start date prior to Treatment Start Date
After Treatment Start	Partial date indicates CMD start date after Treatment Start Date
Uncertain	Partial date insufficient to determine relationship of CMD start date relative to Treatment Start Date
Imputation Calculation	
(A)	15MONYYYY
(B)	01MONYYYY
(C1 or C2)	IF relative reference start = before treatment start THEN TRTSDT-1 ELSE IF relative reference start = ' ' THEN TRTSDT+1
(D)	01JULYYYY
(E)	01JANYYYY

Concomitant medication end date imputation

If not ongoing then -

Imputed date = date part of CMENDTC, if complete date

Imputed date = min(visit 299 date, DEC 31) , if month is missing, (C2, D, E)

Imputed date = min(visit 299 date, last day of the Month) , if day is missing. (A, B, C1)

Concomitant medication date flag

If not a complete date then

Y - If year of the imputed date is not equal to YYYY else

M – If month of the imputed date is not equal to MON else

D

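### Medications are split at randomization, but uncertain start dates flagged as pre-treatment are imputed to the day before first dose, so some pre-treatment drugs are not dated as prior and some ACEI/ARB records can start after they stop

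*Protocol*

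**What the plan says.** Protocol 9.3 and SAP 2.4.2 divide medications at the same point. The protocol has them "prior to and after the randomization date respectively, will be summarized by therapeutic class"; the SAP has them "prior to and after the randomization date respectively, will be summarized by treatment group". SAP 2.4.2 adds that "concomitant medication will be identified based on recorded or imputed start and end dates of medication taking", so the imputation rules feed directly into the split.

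Those rules, in SAP 5.1.3, refer to treatment start (TRTSDT), not randomization. Where a partial start date cannot be placed before or after treatment start (cells C1 and C2), the legend reads "IF relative reference start = before treatment start THEN TRTSDT-1". With a blank flag it gives the day after treatment start instead.

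The two dates differ by design. Protocol 3.1 states: "First application of study drug is planned on the day after Visit 3". Randomization is at Visit 3, and the last ACEI or ARB intake is planned for the evening before it. Protocol 3.1 also foresees a longer gap: "If the patient continued to take their usual ACEI, the start of study drug has to be postponed to assure a 36 hour washout".

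**The concern.** One rule splits the records at one date, and another creates dates by reference to a later one. A drug that the site marked as started before treatment should count as prior therapy, yet the rule can place its start on or after the randomization date. For the pre-study ACEI or ARB, which every eligible patient must have been taking, the imputed start can also fall after the recorded stop.

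At stake are the by-arm tables of prior and concomitant medication. Readers of a comparison of LCZ696 with enalapril will use them to judge background therapy and ACEI/ARB use, and records with a start after the stop would need ad hoc repair at programming.

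A secondary point concerns the split itself. ACEI intake between randomization and a postponed first dose is shown as post-randomization. It may also enter the ACEI and ARB class summaries that SAP 2.4.2 plans for the double-blind period, because the one place where the SAP dates that period (2.8.4.2, vital signs) starts it at Visit 3. The prohibition in protocol 5.5.9 runs only from the start of investigational treatment.

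**Working it through.** The plan gives no figure on this point, so there is none to reproduce. The check is date logic.

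**Inputs.** Split date: randomization, V3 (protocol 9.3, SAP 2.4.2). Imputed start for a flagged C1/C2 record: TRTSDT-1 (SAP 5.1.3). Planned first dose: V3+1, and planned last ACEI/ARB intake: the evening of V3-1 (protocol 3.1). ACEI wash-out: 36 hours (protocol 3.1). Study drug times: about 08:00 and 19:00 (protocol 5.5.4). I assume the same clock times for the ACEI.

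**Step 1: which partial start dates reach C1 or C2.**
- Year missing: C1 if the month is known, C2 if not. The text above the matrix says missing start dates are not imputed, so the cell with both missing is unclear.
- Treatment year, month missing: C2.
- Same month and year as treatment start: C1.
- Earlier month in the treatment year, or earlier year with month known: rule A, the 15th of that month.
- Earlier year, month missing: rule D, 1 July of that year.

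On the planned schedule, rules A and D give dates before randomization. Complete dates are not imputed.

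**Step 2: where TRTSDT-1 falls.** TRTSDT is the date of the first dosing time at least 36 hours after the last ACEI intake, and no earlier than V3+1.

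| Last ACEI intake | Plus 36 h | First dose | TRTSDT-1 | Days from V3 | Days after last intake |
|---|---|---|---|---|---|
| V3-1, 19:00 (planned) | V3+1, 07:00 | V3+1, 08:00 | V3 | 0 | 1 |
| V3, 08:00 | V3+1, 20:00 | V3+2, 08:00 | V3+1 | 1 | 1 |
| V3, 19:00 | V3+2, 07:00 | V3+2, 08:00 | V3+1 | 1 | 1 |
| V3+1, 08:00 | V3+2, 20:00 | V3+3, 08:00 | V3+2 | 2 | 1 |

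In the planned row, a flagged C1/C2 drug is dated on the randomization day, which is not before it. In the postponed rows it is dated after randomization.

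**Step 3: the pre-study ACEI or ARB.** With the protocol's example, Visit 3 is Wednesday, the last intake Tuesday and the first dose Thursday. If the start is recorded as the treatment year with the month missing and the flag is set, cell C2 gives Wednesday, one day after the Tuesday stop. The same follows for a missing year, if that is imputed. The same-month cell cannot apply to an eligible patient: inclusion criterion 5 requires at least 4 weeks of stable dose before Visit 1, and Visit 1 is at least 12 days before Day 1, so the start lies at least 28 + 12 = 40 days back, more than one calendar month.

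**Step 4: the same records with first dose as the cut-off.** TRTSDT-1 is always before TRTSDT, so every flagged C1/C2 drug is prior. Capping the start at the recorded end date puts the ACEI in Step 3 at Tuesday for both start and stop, so the order is possible and the record is prior-only. ACEI intake in the postponed rows is also prior.

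**The case against.** The best reply is that this is a one-day mismatch in descriptive tables, reached only through uncommon records. Several parts of it stand.

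- Neither document says on which side the randomization day falls. If it counts as prior, the misclassification disappears on the planned schedule and remains only when first dose is postponed. The start-after-stop record remains in either case.
- SAP 2.4.2 uses end dates as well as start dates. An ACEI with an impossible start still has a recorded end before Visit 3, so a program that checks the end date may class it correctly.
- ACEI/ARB use is an eligibility criterion, and protocol 8.1 requires full verification of those criteria. A site unable to give the start month should be uncommon.
- Protocol 9.3 separately tabulates CHF background drugs (aldosterone antagonists, beta-blockers, ivabradine, diuretics, digoxin) at baseline and during the double-blind stage, so part of the background picture does not depend on this split.

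A reader might go further and infer that pre-dose ACEI intake is wrongly counted as prohibited use. The documents do not support that. Intake after Visit 3 really is after the randomization date, and no imputation is involved. On the planned schedule it does not arise, because intake stops the evening before. Protocol 5.5.9 sets its own clock for prohibited use, and the ATC table in SAP 2.4.2 lists the renin-angiotensin group for the prior period only. What remains is a presentational weakness: the class list in the same section includes ACEI and ARBs during the double-blind period without saying that pre-dose intake is excluded.

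**Conclusion.** Wrong as written, minor. Applied literally, the SAP's imputation rule conflicts with its split date. A flagged C1/C2 drug is dated on the randomization day, or after it if dosing is postponed, and an ACEI/ARB record of the kind in Step 3 starts one day after it stops.

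Three broader readings are tempting but not supported:
- That drugs known to predate treatment generally drop out of the prior category. Complete dates and rules A and D are unaffected, and the flag must also be set.
- That post-randomization therapy is over-counted through imputation. A drug still taken after Visit 3 belongs there whatever its imputed start.
- That a given number of patients is misclassified. The documents give no count of partial dates. Assuming that 5% to 10% of the 200 patients have such a record gives 10 to 20 patients, but this is only an illustration, and not every such record would end up in the wrong table.

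The effect is confined to descriptive prior and concomitant medication tables. The primary analysis, alpha, sample size and analysis sets are untouched, and nothing in the documents suggests that the error would differ by arm. The conclusion assumes that SAP 5.1.3 is programmed as written; the internal convention it cites (RAP Module 8) was not available to check.

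**What to change.** Make the change in the SAP and list it in SAP section 4 as a change to the protocol-specified analysis.

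1. In SAP 2.4.2, use the first-dose date (TRTSDT) as the single cut-off. Prior means started before first dose; concomitant means taken on or after first dose; prior-only means stopped before first dose. A drug started before and continued is both prior and concomitant. Apply the same cut-off to the double-blind-period class summaries, so that ACEI intake between randomization and a postponed first dose is shown as pre-dose.
2. In SAP 5.1.3, rules C1 and C2, set a start flagged as before treatment to the earlier of TRTSDT-1 and the recorded end date.
3. State whether a record with both month and year missing is imputed, since the text and the matrix in SAP 5.1.3 disagree.

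First dose is the natural anchor: baseline (protocol 9.2, SAP 2.1.1), exposure (SAP 2.4.1), the prohibition in protocol 5.5.9 and the imputation itself already refer to it.

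The cap does not help where the end date is itself partial. A missing end day is imputed to month end or the visit 299 date, whichever is earlier, and could still carry a pre-dose ACEI past first dose. Those records should be listed for review.

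The cost is a few sentences in the SAP and minor derivation code, with no new data and no change to any treatment or wash-out rule.
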